#### Exclusion criteria

1. Patients who had a diagnosis of any HT complications defined by relevant ICPC-2 and/or ICD-9-CM diagnosis codes (defined in the "Methods" section) on or before baseline\*
2. Patients diagnosed to have Diabetes Mellitus (DM) on or before 31 March 2017, defined by ICPC-2 codes of T89 or T90
3. Patients exclusively managed by Specialist Out-Patient Clinic (SOPC) on or before baseline\*

To reduce selection bias, the RAMP-HT and usual care subjects will be matched in baseline covariates using the propensity score matching method:

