#### *Baseline Covariates*

The covariates are categorized into demographics, co-morbidities, clinical parameters and treatment modalities. Demographics include sex, age, smoking status and whether the patient is a recipient of Comprehensive Social Security Assistance (CSSA). Co-morbidities include history of chronic lung disease, cancer or psychological condition indicated by the presence of the relevant ICPC-2 or ICD-9-CM codes in the CMS. These factors reflect the patient's baseline health status. Clinical parameters data including blood pressure (systolic and diastolic), lipid profile (including triglyceride level) and

body mass index (BMI) and treatment modalities including hypertensive drug(s) and lipid-lowering agent(s) used account for HT disease severity and individual CVD risk.

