**HA CMS Data Extraction of Incidence of HT Complications and All-cause Mortality**

Our RAMP-HT QOC study will have collected anonymous 3-year follow up HA CMS data of the cohorts available by November 2015. This study plans to extend the follow up period for an additional 2 years to measure the 5-year incidence of CVD, ESRD and mortality outcomes of these HT patient cohorts from 1 Oct 2011 to 31 March 2017. The data extraction will be carried out by the HA statistics team. Each patient in the cohorts (RAMP-HT and usual care groups) will be observed from baseline to the first occurrence of any of the outcome events until 31 March 2017, with CMS documented diagnoses defined by the relevant ICPC-2 and ICD-9-CM codes below:

1. Cardiovascular disease (CVD) is defined as the presence of any of coronary heart disease (CHD), heart failure or stroke. CHD includes all ischaemic heart disease, myocardial infarction (MI), coronary death or sudden death as indicated by the ICPC-2 K74 to K76 or ICD-9-CM 410.x, 411.x to 414.x, 798.x codes. Heart failure is defined as the ICPC-2 K77 or ICD-9-CM 428.x codes. Stroke (fatal and non-fatal stroke) is defined by the ICPC-2 K89 to K91 or ICD-9-CM 430.x to 438.x codes.
2. End Stage Renal Disease (ESRD) is defined by any of ICD-9-CM 250.3x, 585.x, 586.x, or an estimated Glomerular Filtration Rate (eGFR)  $<15\text{mL/min}/1.73\text{m}^2$ , according to the definition of the National Kidney Foundation.
3. Mortality is defined by a documented death in the Hong Kong Death Registry.

The definitions of each HT complication are determined by the clinician co-investigators and endorsed by clinicians of the HA.

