**Long Term Effectiveness of RAMP-HT**

Descriptive statistics will be performed on the clinical parameters (e.g. blood pressure (BP), lipid profile, BMI) and incidence of CHD, heart failure, stroke, ESRD, HT-related mortality and all-cause mortalities of the RAMP-HT and usual care cohorts. Differences in each outcome between groups will be tested using independent t-tests for continuous variables such as mean BP, or chi-square tests for categorical variables such as proportion of patients with BP control or CVD incidence. The number needed to treat to reduce one CVD, each specific HT complication and death by RAMP-HT will be calculated from the unadjusted 5-year rates between RAMP-HT and usual care HT cohorts.

Multivariable Cox proportional hazards regression will be performed to estimate the adjusted effect of RAMP-HT on the dependent variable of each first HT complication event, adjusting for all baseline covariates of patients. Cox model has been widely used to evaluate the effectiveness of primary care intervention in previous study. For each model, survival curves will be estimated by Kaplan-Meier method and the differences between RAMP-HT and usual care groups will be compared using the

log-rank test. The effectiveness of RAMP-HT will be measured by Hazard ratio with 95% confidence intervals in the regression models. Predictive accuracy of Cox models will be assessed and compared using Harrell's discrimination C-index, ranging from zero to one. A value of 0.5 indicates no predictive discrimination, and values of 0 or 1.0 indicate perfect separation of patients. Goodness-of-fit for Cox regression model will be assessed using Akaike information criterion and Bayesian information criterion.

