The Markov models will be analysed by the TreeAge Pro Suite (TreeAge Software, Inc, Williamstown, MA) which can run Markov models.

Data sources are summarized in the table below:

Propose	Item/ unit	Data collection methods
Effectiveness	Incidence of CVD, ESRD and all-cause mortality	Anonymous 5-year dataset of diagnosis record (ICPC-2 and ICD-9-CM) to be extracted by HA statistics team from the HA CMS database #
Direct Medical Costs	(i)Cost of RAMP-HT	(i) In-depth costing of RAMP-HT by 

- set-up and operation costs questionnaires to be completed by HA clusters, GOPCs

- central administration cost questionnaire completed by

	
(ii)Public medical costs of RAMP-HT and usual care group; with complications and without complications
 
(iii)Private direct medical costs
	
Finance Office in HA Head Office
 
(ii)Public healthcare service cost will be estimated by the products of :
 
 
- Public healthcare service utilization rates will be extracted from the 5-year HA CMS dataset.
 
- Unit cost of each healthcare service published in the HKSAR Government Gazette
 
 
(iii)Private medical cost questionnaire administered by telephone survey on 230 RAMP-HT and 218 usual care HT subjects

Calculation of quality adjusted life years (QALY)	SF-6D Health preference values of HT patients without and with complications	SF-12v2 HRQOL data from 410 RAMP-HT and 388 usual care HT patients collected in our previous PRO surveys from May 2013 to March 2014 will be converted to SF-6D preference values.
Cohort Life-time Mortality estimates	
(i) HT related mortality
 
(ii) Mortality from other causes
	
(i)Annual HT-related mortality rates will be estimated from the annual incidence of HT complications and published mortality rates of the respective complications.
 
(ii) Hong Kong standard life table will be used as a

		benchmark for the estimation of mortality from other causes adjusted for age and sex)
--	--	---------------------------------------------------------------------------------------

The Markov modelling will run on the following assumptions:

1. Each HT patient will develop only one HT complication in his/her lifetime.
2. HT patients without complications will not die from HT related death, but may die from other cause of death.

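### The diabetes exclusion uses ICPC-2 codes only, so patients whose diabetes is coded only in ICD-9-CM stay in a cohort meant to be free of diabetes

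*Combined protocol and SAP*

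**What the plan says.** Section d(ii), Exclusion criteria, item 2 removes "Patients diagnosed to have Diabetes Mellitus (DM) on or before 31 March 2017, defined by ICPC-2 codes of T89 or T90". It names no ICD-9-CM code, drug or laboratory criterion.

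Elsewhere the plan draws on both coding systems:

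- Exclusion item 1, directly above, removes "Patients who had a diagnosis of any HT complications defined by relevant ICPC-2 and/or ICD-9-CM diagnosis codes".
- Baseline Covariates defines the co-morbidities as "indicated by the presence of the relevant ICPC-2 or ICD-9-CM codes in the CMS".
- The section on HA CMS data extraction identifies outcome events "with CMS documented diagnoses defined by the relevant ICPC-2 and ICD-9-CM codes below". Coronary heart disease, heart failure and stroke each have ICPC-2 and ICD-9-CM codes.
- The data source table in the Markov modelling section describes the effectiveness data as "Anonymous 5-year dataset of diagnosis record (ICPC-2 and ICD-9-CM").

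On covariates, the plan states "Co-morbidities include history of chronic lung disease, cancer or psychological condition", and "treatment modalities including hypertensive drug(s) and lipid-lowering agent(s) used account for HT disease severity and individual CVD risk". Diabetes, glucose measures and glucose-lowering drugs are not listed. The Cox model is fitted "adjusting for all baseline covariates of patients", which is the same set.

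**The concern.** The study population is meant to be hypertensive patients without diabetes. The rule that enforces this reads one of the two code sets that the study holds, so diabetes recorded only in the other set does not trigger the exclusion. Because the design relies on exclusion to deal with diabetes, nothing later in the plan handles it directly: it is absent from the propensity score and from the Cox adjustment set.

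Two things are at stake. First, diabetes is taken here to raise CVD risk (an assumption, ranged under the working). If patients who slip through are more common in one arm, the CVD comparison is confounded by a factor the investigators intended to remove. Second, even if they are evenly spread, the observed event rates and costs, and the Markov inputs taken from them, describe a population that differs slightly from the one stated.

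**Working it through.** The plan gives no figure for this point, so there is none to reproduce. The check is a comparison of the text followed by an illustration of scale.

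**Code systems by item**

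| Item | ICPC-2 | ICD-9-CM |
|---|---|---|
| Hypertension (inclusion 2) | K86 | none |
| Hypertension complications (exclusion 1) | yes | yes |
| Diabetes (exclusion 2) | T89, T90 | none |
| Co-morbidity covariates | yes | yes |
| CVD outcomes | yes | yes |
| ESRD outcome | none | yes, or eGFR below 15 |

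Exclusion 1 and the co-morbidity histories already require ICD-9-CM diagnoses up to baseline to be searched. The information needed to close the gap is therefore of a kind the study already handles.

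**Does another criterion close the gap?** Inclusion 2 guarantees that each subject has an ICPC-2 code for hypertension. It does not guarantee that a subject's diabetes is in ICPC-2. Exclusion 3 removes only patients managed exclusively in specialist clinics. Patients seen in both settings remain, and the costing section counts specialist visits and hospital admissions for the cohorts. Both criteria may make the gap small, but neither closes it.

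**Scale.** Inputs:

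- Usual-care 5-year CVD incidence 8% and planned difference 1 point (8% against 7%), from Sample size calculation.
- Share of missed diabetic patients, pR in RAMP-HT and pU in usual care: not in the documents, assumed.
- CVD risk ratio for diabetes, RR: not in the documents, assumed 1.5 to 2.5.

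With no true programme effect and usual care held at 8%:

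RAMP-HT risk = 8% × [1 + pR(RR − 1)] / [1 + pU(RR − 1)]

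spurious difference = 8% − RAMP-HT risk

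For pR = 0, pU = 1%, RR = 2: 8% / 1.01 = 7.921%, a difference of 0.079 points.

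| pR | pU | RR 1.5 | RR 2 | RR 2.5 |
|---|---|---|---|---|
| 2% | 2% | 0 | 0 | 0 |
| 0 | 1% | 0.040 | 0.079 | 0.118 |
| 0 | 2% | 0.079 | 0.157 | 0.233 |
| 0 | 5% | 0.195 | 0.381 | 0.558 |

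(percentage points, in favour of RAMP-HT)

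If the excess is in RAMP-HT instead, the sign reverses. With pR = 1% and pU = 0, the difference is 8 × 0.01 × (RR − 1) = 0.04, 0.08 and 0.12 points against RAMP-HT. In either direction, a 1-point excess amounts to about 4% to 12% of the planned 1-point difference. In the matched cohorts of 8,681, one percentage point is about 87 patients (0.01 × 8,681).

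**The case against.** The strongest case on the other side is that this is an asymmetry of wording with no demonstrated consequence. Several parts of it stand.

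- A reader might infer that diabetes is the one diagnosis handled in a single system. It is not: hypertension is defined by ICPC-2 only, and ESRD has no ICPC-2 code. The inconsistency is with complications, co-morbidities and CVD.
- A missed patient must already be in the ICPC-2 system through the hypertension code, must not be managed exclusively in specialist clinics, and must never have received T89 or T90 up to 31 March 2017, about five years after baseline. The documents do not show that any such patient exists, so the gap may well be small.
- A reader might infer that RAMP-HT's standardised assessment makes the leakage differ between arms. That mechanism is weak. Assessment affects whether diabetes is detected, and diabetes that was never diagnosed has no code in either system. Nothing in the documents shows that patients coded only in ICD-9-CM are spread unevenly.
- The missing covariate is not a separate flaw. Diabetes is presumably left out because it is an exclusion, and its absence matters only to the extent that the exclusion is incomplete. The matched and adjusted BMI, lipids, blood pressure and lipid-lowering drugs may also absorb part of any imbalance.
- Adding ICD-9-CM codes up to 31 March 2017 could do harm. A code first recorded during follow-up may have been entered at an admission for an outcome event, so excluding on it would remove patients in a way that depends on the outcome.

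The selection flow chart (Appendix C) and data schema (Appendix F) are not in the text available and may carry fuller code lists. None of this changes the fact that the stated rule leaves these patients in and that no text available closes the gap.

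**Conclusion.** The point holds as an incomplete exclusion rule that is cheap to repair. Exclusion 2 as written does not remove patients whose diabetes is coded only in ICD-9-CM, and diabetes is not otherwise controlled directly.

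The documents do not support the stronger conclusion that the primary CVD comparison is biased. The number of patients affected, any imbalance between arms and the direction of any bias are all unknown, and balanced leakage gives no spurious difference. On assumed values (an excess of 1 point in one arm, a risk ratio of 1.5 to 2.5, no true effect), the shift is 0.04 to 0.12 points on a planned difference of 1 point. Reaching 0.20 to 0.56 points takes an assumed excess of 5 points, for which the documents offer no evidence. This is a worthwhile improvement and does not threaten the study's validity on present information.

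**What to change.** Add ICD-9-CM diabetes codes dated on or before baseline to exclusion 2, using the plan's own baseline dates (RAMP-HT enrolment, or 31 March 2012 for usual care). Report how many patients the added codes identify in each arm. Drop them before matching or, if the existing 8,681 matched pairs are kept, repeat the main analysis without the affected pairs. Do not apply the added codes to diagnoses first recorded after baseline.

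The timeline already sets aside April to July 2016 for confirming the data schema and operational definitions with the HA statistics team, which is the natural point to make the change. The cost is one more code list and a small loss of pairs; for example, about 87 of 8,681 if 1% of one arm is affected. If the count per arm proves negligible, one sentence in the report settles the matter.

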#### *Baseline Covariates*

The covariates are categorized into demographics, co-morbidities, clinical parameters and treatment modalities. Demographics include sex, age, smoking status and whether the patient is a recipient of Comprehensive Social Security Assistance (CSSA). Co-morbidities include history of chronic lung disease, cancer or psychological condition indicated by the presence of the relevant ICPC-2 or ICD-9-CM codes in the CMS. These factors reflect the patient's baseline health status. Clinical parameters data including blood pressure (systolic and diastolic), lipid profile (including triglyceride level) and

body mass index (BMI) and treatment modalities including hypertensive drug(s) and lipid-lowering agent(s) used account for HT disease severity and individual CVD risk.

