#### *Propensity Score Matching*

Propensity score matching was first introduced in 1983. The technique summarises relevant baseline characteristics of each eligible HT patient into a single-index variable (the propensity score); HT patients in usual care will be matched to patients in the RAMP-HT group based on the value of the propensity score. The propensity score will be generated for each patient by logistic regression, modelling the RAMP-HT as dependent variable and baseline covariates of patients as independent variables. The propensity score mapping will be performed by using the “psmatch2” command with one-to-one matching without replacement and a callipers of 0.001 approach in the STATA.

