#### *(ii) Direct Medical Costs of HT patients*

The medical cost analysis will focus on the direct medical costs involved in the care of HT patients without or with specific HT complications (i.e. CHD, heart failure, stroke and ESRD) in both public and private healthcare sectors; indirect cost (e.g. opportunity cost) and non-medical costs (e.g. transportation cost, carer cost) will not be measured.

Public medical costs will be estimated from products of the unit costs (published in the HKSAR Government Gazette and Hospital Authority ordinance (Chapter 113) of charges for non-entitled persons) and the utilization rates of 1) dispensed drugs (*note: self-financed drugs will be considered as private medical cost, see below*), 2) laboratory tests and investigations, 3) healthcare services including general outpatient clinics (GOPC), specialist outpatient clinics (SOPC), allied health services (e.g. dietician, physiotherapist or occupational therapist), accident and emergency (A&E) department and 4) admissions to hospital in the 12 months before baseline and at 12, 24, 36, 48 and 60 months after study enrolment for each patient in the study cohorts. The data extraction will be carried out by the HA statistics team.

Private direct medical costs include the cost of all private Western doctor and Chinese medicine practitioner consultations, private hospitalisation and self-medications inclusive of self-financed medications prescribed by the HA. 598 HT patients (307 RAMP-HT patients and 291 usual care patients) who were recruited from HA GOPCs for the longitudinal evaluation of patient reported outcomes (PRO) in the evaluation of QOC RAMP-HT study from May 2013 to March 2014 will be invited to complete a “private medical cost of HT questionnaire” (Appendix E) by telephone. The questionnaire is adapted from the costing questionnaire that was used in our in-depth study on the cost-effectiveness analysis of RAMP-DM that had proven feasibility and validity (HHSRF # EPC\_HKU-1A).

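### The matching and Cox covariates leave out prior-year service use, which the plan already extracts, and do not list renal function; this leaves possible residual confounding of unknown size and direction.

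*Combined protocol and SAP*

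**What the plan says.** All references are to the combined protocol and SAP.

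- **d(ii), Baseline Covariates.** "The covariates are categorized into demographics, co-morbidities, clinical parameters and treatment modalities". Demographics are sex, age, smoking and social security status. On co-morbidities: "Co-morbidities include history of chronic lung disease, cancer or psychological condition". On clinical measures: "Clinical parameters data including blood pressure (systolic and diastolic), lipid profile (including triglyceride level) and", with BMI named next. Treatment covers antihypertensive and lipid-lowering drugs.
- **d(ii), Propensity Score Matching.** The score comes from a logistic regression "modelling the RAMP-HT as dependent variable and baseline covariates of patients as independent variables". No balance check is specified there.
- **d(ii), Sample size calculation.** The 8,681 pairs have already been matched and will be the study subjects.
- **d(iv), Direct Medical Costs of HT patients.** Use of drugs, laboratory tests, general and specialist clinics, allied health, emergency departments and hospital admissions is taken "in the 12 months before baseline and at 12, 24, 36, 48 and 60 months after study enrolment for each patient in the study cohorts". Costing is the stated purpose.
- **d(iv), HA CMS Data Extraction.** CVD is identified from diagnosis codes in the clinical system. ESRD is identified from codes or from an eGFR below 15.
- **d(v), Long Term Effectiveness.** The Cox models estimate the programme effect "adjusting for all baseline covariates of patients". CVD incidence is also compared by chi-square, and the number needed to treat uses unadjusted 5-year rates.

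**The concern.** Usual-care patients are those who never enrolled in the programme up to 31 March 2017, and events are found through coded records. How often a patient attended before baseline could therefore bear on who was enrolled, and on whether an event was recorded. Prior admissions may also mark underlying risk. Renal function is a natural covariate when ESRD is an outcome. The complication exclusion is worded by diagnosis codes only, so an uncoded low eGFR at baseline is not ruled out.

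Because the Cox models reuse the matching covariates, no later step recovers what the match left out. The chi-square comparison and the number needed to treat rest on the match alone. The CVD and ESRD hazard ratios also set the programme arm's transition probabilities for the first five years of the Markov model. Any residual confounding would therefore reach two of the three primary outcomes: CVD incidence and the cost-effectiveness ratio.

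**Working it through.** **Plan's own figure.** The plan gives none for confounding. The relevant planning values are in the sample size section: 5-year CVD incidence of 7% (RAMP-HT) and 8% (usual care), observed 1-year incidence of 1.33% and 1.76%, and 8,681 patients per group. (The stated minimum of 7,116 per group is not reproduced by the usual two-proportion formula, which gives 14,577 at two-sided 5% and 90% power. That is a separate matter and does not bear on this point.)

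**Covariate check.** Prior service use fits none of the four categories. eGFR and creatinine appear under neither co-morbidities nor clinical measures.

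**E-value.** This is the smallest risk ratio that an omitted factor would need with both programme entry and CVD, beyond the measured covariates, to account for the whole effect. With r = 1/RR, E = r + √(r(r − 1)).

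- Planned rates: RR = 0.07/0.08 = 0.875; r = 1.143; E = 1.143 + √(1.143 × 0.143) = 1.55.
- Same rates as a hazard ratio: ln(0.93)/ln(0.92) = 0.870; r = 1.149; E = 1.56.
- Observed 1-year rates: RR = 1.33/1.76 = 0.756; r = 1.323; E = 1.323 + √(1.323 × 0.323) = 1.98.

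**Confidence limit.** With 8,681 per group and pairing ignored, SE of log RR = √(0.93/(0.07 × 8,681) + 0.92/(0.08 × 8,681)) = 0.0534. The 95% interval around 0.875 is 0.79 to 0.97. For the upper limit of 0.972, r = 1.029 and E = 1.20.

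**Range under assumptions.** The documents give no distribution of either factor by arm, so the inputs here are assumed. For an omitted binary factor with prevalence p1 in RAMP-HT and p0 in usual care, and risk ratio R for CVD, the bias factor is B = [1 + p1(R − 1)]/[1 + p0(R − 1)], and the adjusted ratio is 0.875/B. With p1 = 10%:

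| R | p0 = 12% | p0 = 15% | p0 = 20% |
|---|---|---|---|
| 1.5 | 0.883 | 0.896 | 0.917 |
| 2 | 0.891 | 0.915 | 0.955 |
| 3 | 0.904 | 0.948 | 1.021 |

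Example: R = 2 and p0 = 15% give B = 1.10/1.15 = 0.957, and 0.875/0.957 = 0.915.

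If the factor is instead more common in RAMP-HT, swapping the two prevalences inverts B and the adjusted ratio becomes 0.875 × B. The corners are 0.875 × 0.991 = 0.867 and 0.875 × 0.857 = 0.750. The assumed range is thus 0.88 to 1.02 one way and 0.87 to 0.75 the other.

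**The case against.** **Availability of eGFR.** A reader might infer that baseline eGFR is already in hand. The documents do not show this. eGFR appears only as a threshold in the ESRD outcome, laboratory tests are extracted as use to be costed, and the data schema (Appendix F) is not in the text available. The clinical list is also introduced as inclusive, so eGFR may not have been ruled out. Baseline values may be more complete in RAMP-HT, whose patients have standardised complication screening, than in usual care. This objection stands for eGFR. It does not help service use, which has no category and is explicitly extracted.

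**Direction.** A reader might infer that the omission could explain away the benefit through clinic contact. If more contact leads to more enrolment and more coded CVD, the bias runs against RAMP-HT and cannot produce a benefit. Explaining one away needs a factor that raises CVD and is less common in RAMP-HT, and no section reports such an imbalance.

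**Existing control.** Coded complications, diabetes and exclusively specialist care are excluded. Age, blood pressure, lipids, co-morbidities and drugs are matched and then adjusted for again. These may capture part of both factors; how much is unknown.

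**Choice of rates.** The plan itself calls 7% versus 8% conservative, and the observed 1-year rates give the larger E-value. Both should be quoted.

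**Conclusion.** The point holds as an avoidable gap in adjustment. It is not a demonstration of bias. Leaving out prior-year service use is clear on the text and needs no new data to repair. The absence of renal function is clear from the list, but whether baseline eGFR is held is not stated.

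The planned effect is small, so modest residual confounding could matter: the E-value is about 1.55 at the planned rates, about 2.0 at the observed 1-year rates, and about 1.20 for the planning-based upper confidence limit. These say how strong a factor would have to be beyond the measured covariates; they do not show that either omitted factor is that strong. The ranges of adjusted ratios rest wholly on assumed prevalences and risk ratios. Whether the 8,681 pairs are imbalanced on either variable, and in which direction, cannot be told from the documents.

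**What to change.** 1. Keep the 8,681 matched pairs. Re-matching is not shown to be cheap: the pairs are already fixed, the stated pre-baseline extraction covers only patients in the study cohorts, and a new match could change the number of pairs.
2. Add general clinic, specialist clinic, emergency and inpatient use in the 12 months before baseline to every multivariable Cox model.
3. State whether baseline eGFR is held. Where it is, add it to the same models and report its missingness by arm.
4. Report standardised differences for both variables in the matched pairs.
5. If either is imbalanced, report covariate-adjusted 5-year risks and number needed to treat beside the unadjusted ones.

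The cost is a little more analysis, with no new data collection for service use. The main downside is that baseline eGFR may be unevenly available between arms, which is why its missingness should be shown.
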